- a) Participants will again be reminded that they will be contacted by text message (preferred) or phone on a scheduled basis as each week progresses. Reminder

Date: 01/10/2024

Principal Investigator: [name]

Application Number: IRB00224186

of the two offered dates & times of the following week's study visit. The participant will choose one of the two dates for the study visit. Reminders will be sent 72 hours and 24 hour prior to each phone call or videoconference.

b) For those prescribed Chantix®, follow-up will again occur every 72 hours. The text or phone messages will ask if experiencing any medical issues on therapy [See Drugs/Substances/Devices and Risks sections in this protocol for more information on adverse effects]. The text messages will state the question, "Are you experiencing any side effects or are you having any problems with taking Chantix?" If they text back "Yes", the participant will receive a phone call by our research staff. The concerns will be reviewed with our medical specialists. The medical specialists may call the participant for further details and/or relaying the treatment plan. Concerns about the clinical status may warrant referral to the JHH Emergency Room or the Tobacco Treatment Clinic at Bayview Medical Center if acute medical care concerns arise.

- If the medical recommendation is to discontinue BOTH the "acute" and "controller" pharmacotherapy, the patient will be disenrolled from the study. They will be provided contact information of local smoking cessation resources. They will be provided information for the state quit line ([name]) and the Tobacco Treatment Clinic at Bayview Medical Center. Participants who are disenrolled will be contacted by phone at the end of the intervention to employ the final survey used at the time=+4 week point (See "**Supplementary Document 3**")

Participants will again be provided with a 24-hour phone contact to communicate with our research team. Participants will be able to text regarding any concerns about the study. Participants will receive a text and/or voice response to the identified within 1 day of receipt. All concerns will be documented and reviewed with the PIs and/or identified medical specialists of the research team.

TIME POINT 5 – follow/up visit

WEEKLY FOLLOW-UP VISIT

All elements of this time point mirror the description represented above (TIME POINT 4). The only difference is that one interval text messaging type will be used. *We will no longer ask Chantix® users about medication concerns every 72 hours, if they have not reported any adverse effects to date on therapy.* Participants will continue to receive reminders at 72 hours and 24 hours prior to the next scheduled follow-up study visit.

TIME POINT 6 – follow/up visit

WEEKLY FOLLOW-UP VISIT

All elements of this time point mirror the description represented above (TIME POINT 5)

TIME POINT 7 – FINAL follow/up visit

FINAL VISIT

This final study visit will occur by videoconference (Zoom) or a phone call. Two separate times for the study visit will be offered to allow participants the option to choose a time more

Date: 01/10/2024

Principal Investigator: [name]

Application Number: IRB00224186

preferable to their schedule. The intervention at this time point will have 3 key features:

1. Survey completion that contains questions about smoking characteristics and completion of open-ended questions that explore the feasibility of the study pilot (see “Supplementary Document 3”).
2. Referral to [name] or Tobacco Treatment Clinic at Bayview Medical Center if continued smoking cessation resources are requested
3. \$15 cash equivalent reimbursement for study participation.

1ST STEP – CONFIRMATION AND SURVEY SCREENING

- Participants will check-in with research staff to confirm their enrollment in the study.
- A short survey (approximately 5 minutes) will be undertaken to acquire key smoking characteristics (see “Supplementary Document 3”). The survey will ask the usage & frequency that the prescribed pharmacotherapies are being used, as well as query the degree of nicotine dependence over the 4-week pilot period. Surveys will be displayed on the video conference call if Zoom is the preferred modality for the study. For participants with difficulty reading the survey, the questions will be read aloud and the responses will be recorded. For phone-based visits, our research team will read the questions aloud and record the answer choices.
- Participants will also be asked 10 open-ended questions that will assess study feasibility (see “Supplementary Document 3”). Questions will be read aloud and the responses will be summarized solely in a written format by the research team. The questions explore participant thoughts on the objective, data collection, recruitment, pharmacotherapy experience (administration, education, delivery and monitoring), motivational interviewing, study schedule and text messaging/phone follow-up.

2ND STEP – UNUSED DRUG SUPPLIES

- Participants will be encouraged to return any unused drug supplies. The medications will be able to be returned in a pre-stamped envelope that was provided with the initial medication package prior to the study. The return envelope is to be labelled to the attention of the PI ([name]). The unused medications will be dropped off at a drug disposal unit at Johns Hopkins Monument Street Pharmacy.

3RD STEP – POST-PILOT CESSATION RESOURCES

- All participants will be provided contact information of local smoking cessation resources for continued participation in the cessation effort. They will be provided information for the state quit line ([name]) and the Tobacco Treatment Clinic at Bayview Medical Center.

4TH STEP – REIMBURSEMENT OF STUDY VISIT PARTICIPATION BY EMAIL OR

TEXT MESSAGING.

- \$15 cash equivalent reimbursement for study participation.

• ***Data and Safety Monitoring Plan***

For the proposed research, [name] will take the responsibility for coordinating and assuring data storage and access. We do not expect the project to produce more data than can be appropriately managed by the research team. This research will generate data resulting from surveys and questionnaires.

Clinical Research Management System (CRMS) is being used for data management and research implementation. CRMS will contain the following information:

- Protocol information from eIRB2
- Registry of study participants
- Management of study accruals
- Consent tracking
- Secure location for study-related documents (e.g. surveys, questionnaires and screening tools)
- Pre-configured and adhoc reports
- Multiple interfaces with Epic, including sending data to Epic about the study and the study participants

Written surveys, questionnaires and screening tools completed by participants (or assisted by research staff) will be scanned into CRMS. All written material will be destroyed after scanning has been completed. Files will only be shared with research team members listed on the IRB application.

SAFE, the Secure Analytic Framework Environment, will also be used as a secure environment to analyze and share sensitive data (e.g. PHI) with research staff. Statistical analyses and report generation/sharing will occur on the SAFE network. Data will be stored in SAFE in one of the following formats: Stata, Microsoft Excel, PowerPoint, Microsoft Word and/or Acrobat PDF.

Data analysis will occur individually and collectively in group meetings. Analysis will occur only at JHU. Results may be tabulated and summarized for ease in understanding the analysis. All analysis will occur within SAFE desktop software apps.

Findings of the de-identified data will be used among research team for the development of larger-scaled tobacco intervention studies. Data containing PHI will not be shared outside of the JHU research team. All public discussions and/or scientific publications will use de-identified datasets.

All affiliates within the Housing Authority of Baltimore City will only be provided de-identified, aggregated data.

Data will be maintained on SAFE desktop for five years after the conclusion of the project.

Date: 01/10/2024

Principal Investigator: [name]

Application Number: IRB00224186

- **STUDY DURATION AND NUMBER OF STUDY VISITS REQUIRED OF RESEARCH PARTICIPANTS**

- a) Duration of Study Participation

The total duration of study subject participation is 6 weeks – including screening, consent and intervention phases.

- b) Number of study visits

A total of 6 study visits will occur over the 6-week duration of the study.

- Visit 1: Screening and consent
 - Visit 2: Baseline time point of the intervention (including delivery of pharmacotherapies)
 - Visit 3: Follow-up time point of the intervention
 - Visit 4: Follow-up time point of the intervention
 - Visit 5: Follow-up time point of the intervention
 - Visit 6: Final intervention time point

All participants will be screened, consented, receive their cessation pharmacotherapy and undergo their baseline study visits in-person. All remaining study visits will occur remotely through video conferencing or standard audio phone calls.

- **BLINDING, INCLUDING JUSTIFICATION FOR BLINDING OR NOT BLINDING THE TRIAL, IF APPLICABLE.**

This is a pre-post study design with no active comparator. All participants will receive the intervention. There is no blinding during the trial.

- **JUSTIFICATION OF WHY PARTICIPANTS WILL NOT RECEIVE ROUTINE CARE OR WILL HAVE CURRENT THERAPY STOPPED.**

Not applicable

- **JUSTIFICATION FOR INCLUSION OF A PLACEBO OR NON-TREATMENT GROUP.**

Not applicable

- **DEFINITION OF TREATMENT FAILURE OR PARTICIPANT REMOVAL CRITERIA.**

Participants will be removed if any of the following criteria are met:

- a) Smoking cessation reported at the start of the intervention (BASELINE VISIT)
 - b) Based on reported adverse medication effects, our medical specialists may recommend for discontinuation or modification of the pharmacotherapy regimen.

Date: 01/10/2024

Principal Investigator: [name]

Application Number: IRB00224186

Participants who are recommended to discontinue *BOTH* the “acute” and “controller” pharmacotherapy will be disenrolled from the study.

- **DESCRIPTION OF WHAT HAPPENS TO PARTICIPANTS RECEIVING THERAPY WHEN STUDY ENDS OR IF A PARTICIPANT’S PARTICIPATION IN THE STUDY ENDS PREMATURELY.**

If the participant’s participation ends prematurely, they will receive their reimbursement from their final study visit. They will also be provided the contact information of local smoking cessation resources, include the state quitline ([name]) and Tobacco Treatment Clinic at Bayview Medical Center.

For participants who complete the study, they too will be provided the contact information of local smoking cessation resources, include the state quitline ([name]) and Tobacco Treatment Clinic at Bayview Medical Center.

Subjects may withdraw from the study at any time without impact to their care.

5. **INCLUSION/EXCLUSION CRITERIA**

Inclusion criteria:

1. ≥ 18 years of age
2. Self-reported smoker with either daily or weekly cigarette use, as well as expressed desire to reduce or quit smoking
3. Proof of residence at Douglass or Brooklyn Homes - as confirmed by verbal acknowledgement by the service coordinators at each site.
4. Working mobile phone with texting ability for the duration of the study
5. Active health insurance (for pharmacotherapy billing)

Exclusion criteria:

1. Pregnant – women will verbally acknowledge that they are *not* pregnant or trying to become pregnant in the next 8 weeks from the time of screening and recruitment to ensure no intake of nicotine and non-nicotine pharmacotherapy
2. Breastfeeding – women who are verbally acknowledge they are breastfeeding will be excluded from the study. This exclusion factor is in place secondary to breastfeeding concerns associated with the study’s usage of nicotine and non-nicotine pharmacotherapy
3. Ongoing participation in a tobacco cessation program or related tobacco intervention study. Past participation in previous iterations of the protocol is not an exclusion criteria.
4. No active health insurance.
5. Unable to verbally state that they are willing to reduce or quit smoking upon recruitment and screening
6. Adults lacking capacity to consent
7. Non-English speakers

Date: 01/10/2024

Principal Investigator: [name]

Application Number: IRB00224186

8. Self-reported usage of *only* non-combustible tobacco products, such as smokeless tobacco or Electronic Nicotine Delivery Devices (ENDS).
9. Anticipated relocation outside of Douglass or Brooklyn Homes prior to the final study visit

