8. Pregnant – women will verbally acknowledge that they are *not* pregnant or trying to become pregnant in the next 8 weeks from the time of screening and recruitment to ensure no intake of nicotine and non-nicotine pharmacotherapy
9. Breastfeeding – women who are verbally acknowledge they are breastfeeding will be excluded from the study. This exclusion factor is in place secondary to breastfeeding concerns associated with the study’s usage of nicotine and non-nicotine pharmacotherapy
10. Ongoing participation in a tobacco cessation program or related tobacco intervention study. Past participation in previous iterations of the protocol is not an exclusion criteria.
11. No active health insurance.
12. Unable to verbally state that they are willing to reduce or quit smoking upon recruitment and screening
13. Adults lacking capacity to consent
14. Non-English speakers
15. Self-reported usage of *only* non-combustible tobacco products, such as smokeless tobacco or Electronic Nicotine Delivery Devices (ENDS).

Date: 01/10/2024

Principal Investigator: [name]

Application Number: IRB00224186

16. Anticipated relocation outside of Douglass or Brooklyn Homes prior to the final study visit
17. Clinical condition(s) that serve as absolute contraindications for the usage of NRT and non-NRT products and non-NRT products (Chantix®) (Reference: PMID 36280333)
 - a. Absolute contraindications of NRT products:
 - *NRT gum: Dysphagia and subsequent aspiration risk*
 - *NRT lozenge: Dysphagia and subsequent aspiration risk*
 - *NRT transdermal patch: Severe diffuse skin disease*
 - *Women who are pregnant or breastfeeding.*
 - b. Absolute contraindication of Chantix®:
 - *Inability to swallow pills*
 - *History of serious hypersensitivity or skin reactions to Chantix®*
 - *Women who are pregnant or breastfeeding*

***NOTE 1:** We will cease enrollment at 60 participants. Our aim is to enroll 30 participants at Douglass Homes and 30 participants at Brooklyn Homes. We anticipate that ≈20% of screened participants (12 people) will not continue participation at the start of the intervention. This allows enrollment and follow-up of 48 participants.

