- ❖ Participants will be notified that they will undergo a two-step consenting process that includes a Physician/Mid-level provider consent signature because of the inclusion of a prescription medication. The Physician/Mid-level provider will preferentially acquire consent at the time that the main consent process is being conducted on-site by the research team member. If the Physician/Mid-level provider consent cannot be acquired at the time of the main consent process, the provider will conduct a separate remote encounter to acquire consent. For remote consent to occur by the Physician/Mid-level provider, the designee will sign and place the date/time in the appropriate section of the consent under the observation of the on-site research team member. The provider will be provided the original consent form by the research team member and the member will verbally verify the participant signed the consent. The provider will contact participants by their preferred communication method (phone or video conferencing) to complete the consent. The Physician/Mid-level provider will review any additional study participant questions and discuss the risks, benefits and alternatives of the study in full detail. The Physician/Mid-level provider consent form is then signed, dated/timed by the provider. All components of the consent are combined to one document. After the informed consent process is completed, an IRB approved study team member then files the consent document in CRMS, including a note confirming the consent process. The entire consent document is also then filed in the research record. A copy of the fully completed consent form will be mailed to the participant's home address.

Participants will also be notified during the time of consent that they will be required to return to the same site in which screening & consent had occurred to pick up their prescribed pharmacotherapies. Participants will receive a phone call, text message and/or personally notified by the on-site housing service coordinator of a time and date for the prescription pick-up.

TIME POINT 2

Prescription of nicotine pharmacotherapies:

All participants who complete the screening process will be prescribed two classes of medications:

1. one "acute" or rescue NRT to address immediate nicotine cravings (e.g., NRT gum or lozenges)
2. one "chronic" or long-term controller to address the constant level of nicotine cravings or addiction (e.g., NRT transdermal patch or Chantix®)

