Along with the package of medications, a stamped return envelope (addressed to PI: [name]) will be provided to allow for participants to return unused medications. Medications received by the PI will be dropped off at a drug disposal unit at Johns Hopkins Monument Street Pharmacy.

If the medications cannot be delivered by the study team on the day of pick-up from the Monument Street Pharmacy, the packaged medications will be stored in a locked cabinet in the locked office of [name] (PI). The office is located in the Division of Pulmonary and Critical Care Medicine within the Asthma and Allergy Building ([name]). Temperatures will be recorded in the office at least on a weekly basis to confirm the environment is appropriate for drug-storage.

PART 2 – START OF THE INTERVENTION (BASELINE)

Date: 01/10/2024

Principal Investigator: [name]

Application Number: IRB00224186

There are 4 steps that will occur in the start of the intervention:

1ST STEP – CONFIRMATION AND SURVEY SCREENING

This step includes the following:

- Confirmation that the participant underwent pre-screening in Time Point 1
 - We will confirm that the participant was pre-screened and consented. This confirmation will occur by asking the participant to verbally state their name, date-of-birth and place of residence. This information will be captured during the screening and stored in CRMS.
- Continued self-report of daily cigarette usage
 - If the participant reports that they are no longer smoking cigarettes, they will be provided the contact information of local smoking cessation resources in case they again start to smoke ([name] or Tobacco Treatment Clinic at Bayview Medical Center). The medications will be dropped off at a drug disposal unit at Johns Hopkins Monument Street Pharmacy.
- Baseline survey completion that contains questions about sociodemographic and smoking characteristics (see “Supplementary Document 3”).

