 - Participants will complete baseline surveys that capture sociodemographic and smoking characteristics (see “Supplementary Document 3”). Participants will be allowed sufficient time (no limit) to complete the survey. For participants with difficulty reading the survey, the questions will be read aloud and the responses will be recorded. We anticipate that the survey will take no more than 5-10 minutes to complete since we purposely are acquiring fewer but impactful questions to minimize participant study burden.
- RE-confirmation of any potential contraindications for the prescribed NRT and non-nicotine pharmacotherapies – as chosen during screening. This review of contraindications will occur by our research team.

This step will duplicate the review of absolute and relative contraindications undertaken during the screening process:

- Absolute contraindications of NRT products
 - *NRT gum: Dysphagia and subsequent aspiration risk*
 - *NRT lozenge: Dysphagia and subsequent aspiration risk*
 - *NRT transdermal patch: Severe diffuse skin disease*
 - *Women who are pregnant or breastfeeding.*
- Relative contraindication of non-NRT products:
 - *Recent myocardial infarction (≤ 2 weeks), arrhythmias, angina, ulcers, uncontrolled high blood pressure, overactive thyroid, pheochromocytoma, or a dental condition or disorder.*
- Absolute contraindication of Chantix®:
 - *Inability to swallow pills*
 - *History of serious hypersensitivity or skin reactions to Chantix®*
 - *Women who are pregnant or breastfeeding*

- Relative contraindication of Chantix®:
 - Severe renal impairment (dosage adjustment is necessary)
 - Underlying neuropsychiatric disease
- ***NOTE:** If contraindications are noted, the team will immediately review them with the study's advanced practice provider (physician and/or pharmacist). If contraindications exist and the medical specialists determine the patient is not a suitable candidate any longer for the prescribed pharmacotherapies, the patient will be disenrolled from the study; they will be provided contact information of local smoking cessation resources ([name] and Tobacco Treatment Clinic at Bayview Medical Center). Modifications in acute and controller therapy dosing may be employed in conversations with our team's medical specialists (e.g., transdermal NRT patch in replacement of Chantix®).

2ND STEP – DRUG EDUCATION AND SIDE-EFFECT MONITORING

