7. STUDY STATISTICS

a. Primary outcome variable

The primary endpoint will be study feasibility. Feasibility will be measured using open-ended questions administered by the research team and targeting the study stakeholders (study participants, community stakeholders and research team). The answers will serve as a means to evaluate the need for further modification in the recruitment, screening, consent, study implementation and evaluation phases of future study testing..

b. Exploratory outcome variables

Pre- & post-changes in nicotine dependence levels – Results will be stratified by baseline smoking behaviors, sociodemographic characteristics and socioeconomic stressors. For group-wise comparisons, t-test or analysis of variance will be used. Regression analyses will be performed to investigate the relationship between baseline measures and changes in smoking characteristics as the pilot study progressed.

c. Statistical plan including sample size justification and interim data analysis

Date: 01/10/2024

Principal Investigator: [name]

Application Number: IRB00224186

This study will not be powered for significance. The primary purpose of this study is to assess feasibility of the pilot study design.

d. Early stopping rules

Not applicable

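### About 12 of 60 are expected not to start, but participants get the primary-endpoint questions only at the final visit, with no visible provision to ask non-starters

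*Combined protocol and SAP*

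**What the plan says.** **Numbers.** NOTE 1, after the Time Point 1 eligibility criteria, stops enrolment at 60 (30 per site). It expects that about "20% of screened participants (12 people) will not continue participation at the start of the intervention" and gives 48 as the number enrolled and followed. It allows for no loss after the start.

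**Primary endpoint.** Section 7a names feasibility and states: "Feasibility will be measured using open-ended questions administered by the research team and targeting the study stakeholders". The stakeholders are participants, community stakeholders and the research team. The answers are meant to "evaluate the need for further modification in the recruitment, screening, consent, study implementation and evaluation phases of future study testing". Section 7 does not say when any of the three groups is asked.

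**When participants are asked.** Time Point 7, the final visit, lists "completion of open-ended questions that explore the feasibility of the study pilot" among its features. Its 1st step says: "Participants will also be asked 10 open-ended questions that will assess study feasibility". No other visit contains these questions.

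**Leaving at or before the start.** At consent, participants are told that "they will be required to return to the same site in which screening & consent had occurred to pick up their prescribed pharmacotherapies". Nothing is said about those who do not come. At the baseline visit (Time Point 3, Part 2, 1st step): "If the participant reports that they are no longer smoking cigarettes, they will be provided the contact information of local smoking cessation resources". For those found unsuitable for the prescribed treatment at the same step, "the patient will be disenrolled from the study; they will be provided contact information of local smoking cessation resources".

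**The one exit contact.** The 4th step of Time Points 3 and 4 describes a phone call at the end of the intervention, with the final survey, for participants who are disenrolled. In both places it stands under the bullet on being advised to stop both medications. A note at Time Point 3 says this is not anticipated.

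**The concern.** Feasibility is judged partly by asking participants how the study worked for them, but the plan puts the question only to those who reach week 4. Reaching week 4 is itself part of what feasibility means, so the participants asked are selected on the outcome being judged.

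Section 2 lists recruitment, consent, and the selection and delivery of medication among the objectives. People who leave between consent and the start have been through some of these steps and then stopped, so they can speak directly to early barriers. If they are not asked, the design would tend to look more workable than it was. Changes to recruitment, screening and consent for the next study would be decided on that basis.

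**Working it through.** **1. The plan's figure.** Inputs from NOTE 1: 60 enrolled, about 20% lost at the start.

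- Lost: 0.20 × 60 = 12.
- Remaining: 60 − 12 = 48. Reverse check: 48 / (1 − 0.20) = 60.

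The stated 12 and 48 are reproduced exactly on a base of 60. If 60 were meant to start after a 20% loss, 60 / 0.80 = 75 would have to be screened, which does not fit the stated 12 and 48.

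**2. Exit routes set against the questions.**

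| Route | What the plan provides | Open-ended questions? |
|---|---|---|
| Does not return for pick-up or baseline | No step described | No provision seen |
| No longer smoking at baseline | Cessation contacts | No provision seen |
| Found unsuitable at baseline | Disenrolled, cessation contacts | Only if the exit call is read broadly |
| Advised to stop both medications later | Phone call with the final survey | Probably; supplement not seen |
| Other early end (section 4, premature end) | Reimbursement, cessation contacts | No provision seen |

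The only route with a stated contact is the one the plan does not anticipate. Section 8c treats missed visits and missing outcomes as minor deviations and adds no step to recover the answers.

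**3. Share asked.** If the 60 are consented and all 48 starters reach the final visit, at most 48 / 60 = 80% of participants are asked, and 12 / 60 = 20% are not. If the leavers were included, the target would be 60 / 60 = 100%.

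**4. What 20% unasked can hide.** As an illustration only, suppose the answers were coded favourable or not, which the plan does not specify. If a share p of the 48 were favourable, the share over all 60 lies between 0.8p and 0.8p + 0.2. At p = 0.90 that is 0.72 to 0.92.

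**The case against.** **The gap rests on silence.** The supplementary documents are not in the material reviewed. The exit call cites Supplementary Document 6 at Time Point 3 and Document 3 at Time Point 4, so its content cannot be checked. The word *disenrolled* is also used for people found unsuitable at baseline, so the call may already cover some of the expected leavers. This stands. A reader might infer that the 12 are never asked, but the documents support only that no provision to ask them is visible.

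**The 12 may not be participants.** NOTE 1 calls the same 60 both enrolled and screened, and screening comes before consent. If the 12 are lost before consent, they are not owed an endpoint assessment. The cap on enrolment at 60 and the timing at the start of the intervention favour the other reading, but the text does not settle it.

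**Other sources exist.** The research team and community stakeholders are also questioned. On-site coordinators know the residents, and pick-up is offered on at least two dates with personal notice. The data system tracks accruals and consent, so leavers can be counted. This limits the harm, but reasons supplied by others are second-hand. People removed because they have stopped smoking are also not evidence of a barrier.

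**Later leavers are partly heard.** Weekly surveys ask about medication use and reasons for poor adherence, and participants can text concerns that are documented. A reader might extend the gap in full to everyone lost during the 4 weeks; the documents do not support that.

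**Later loss cannot be sized.** A reader might apply the earlier pilot's 79.5% retention to the 48 starters. That rate is given for those recruited, through to the final week, and 60 × 0.795 = 47.7, close to 48. Applying it after the 20% would probably count the same loss twice. The plan does not say where its 20% comes from, so this is an inference, but it is reason enough not to compound the two.

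**Conclusion.** The point holds as a minor one. Followed as written, the plan draws participants' primary-endpoint answers from those who reach the final visit, and shows no means of asking the people it expects to lose at the start. On the plan's own figure this is up to 12 of 60 (20%); no larger figure is supported.

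This rests on three assumptions: that the 60 are counted at consent, that the unseen supplements contain no exit questions for non-starters, and that the exit call is limited to the bullet in which it stands. If the call is read broadly, the gap shrinks to no-shows, those who had stopped smoking, and others who leave without being disenrolled. If the 60 are counted at screening, some or all of the 12 fall outside the endpoint, and the defect is mainly in NOTE 1's wording.

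No test, power figure or treatment decision is affected, because the study is not powered for significance.

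**What to change.** 1. Extend the end-of-study call already described at Time Points 3 and 4 to every consented participant who does not start, leaves early or misses the final visit, unless they decline contact.
2. In that call, ask the reason for leaving and those open-ended questions that apply up to the point of leaving. Name one supplementary document for it in both places.
3. State in NOTE 1 whether the 60 are counted at screening or at consent.
4. Report participants' answers with the number asked out of the number consented, separately for leavers and completers.
5. Confirm that the consent form permits the contact. Those pages are not in the material reviewed; if permission is missing, one sentence is enough.

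The cost is about 12 short calls on the plan's own figure, plus any later leavers, made by existing staff to people who needed a working mobile phone to be eligible. Some will not be reached, so the gap narrows but does not close. The target of 60, the visits and the treatment are unchanged.
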